## 6 Appendices

### 6.1 Schedule of Assessments

**Table 3. Schedule of Assessments**

	Assessment a	Visit						
		Screening/ Baseline b	Month 6 (±14 d)	Month 12 (±14 d)	Month 18 (±14 d)	Month 24 (±14 d)	Month 30 (±14 d)	Month 36/ET c (±14 d)
Study Entrance & Disease History	Informed consent d	X						
	Eligibility	X						
	Documentation of CSF1R gene mutation	X						
	Medical/family history and demographics	X						
	Prior/concomitant medications/procedures e	X	X	X	X	X	X	X
	Urine drug screen	X						
	Urine pregnancy test (WOCBP)	X	X	X	X	X	X	X
	COVID-19 assessment f	Per SOC	Per SOC	Per SOC	Per SOC	Per SOC	Per SOC	Per SOC
Safety Assessments	C-SSRS g	X	X	X	X	X	X	X
	Physical and neurological examinations	X	X	X	X	X	X	X
	Height and weight	X						
	Adverse events h	X	X	X	X	X	X	X
	Survival assessment i					X		X
Biomarkers	Coagulation for Optional CSF Biomarker Sub-study j	X		X		X		X o
	Blood sampling (for biomarker analysis)	X	X	X	X	X	X	X p
	Optional CSF Biomarker Sub-study k	X		X		X		X o
	Magnetic Resonance Imaging (MRI) l	X	X	X	X	X	X	X q
Cognitive Assessments	MoCA	X	X	X	X	X	X	X
	CDR ® +NACC-FTLD m	X	X	X	X	X	X	X
	BAC	X	X	X	X	X	X	X
	CBFS	X	X	X	X	X	X	X
Motor Assessments	2MWT	X	X	X	X	X	X	X
	TUG	X	X	X	X	X	X	X
Severity of Illness Scales	CGI-S	X						
	CGI-C		X	X	X	X	X	X
	PGI-S	X						
	PGI-C		X	X	X	X	X	X
Functional, Psychiatric & Other Assessments	FAQ n	X	X	X	X	X	X	X
	NPI-12 n	X	X	X	X	X	X	X
	Zarit Burden Interview n	X	X	X	X	X	X	X

Abbreviations: 2MWT = 2-Minute Walk Test, ALSP = adult-onset leukoencephalopathy with axonal spheroids and pigmented glia, BAC = Brief Assessment of Cognition, CBFS = Cortical Basal ganglia Functional Scale, CDR®+NACC-FTLD = Clinical Dementia Rating Scale plus National Alzheimer's Coordinating Center-Frontotemporal Lobar Degeneration, CGI-C = Clinical Global Impression - Change, CGI-S = Clinical Global Impression – Severity of Illness, CSF = cerebral spinal fluid, CSF1R = colony-stimulating factor 1 receptor, C-SSRS = Columbia-Suicide Severity Rating Scale, ET = early termination, FAQ = Functional Activities Questionnaire, LP = lumbar puncture, MoCA = Montreal Cognitive Assessment, NPI-12 = Neuropsychiatric Inventory – 12-Item Version, PGI-C = Patient Global Impression - Change, PGI-S = Patient Global Impression - Severity of Illness, SOC = standard of care, TUG = Timed Up and Go, WOCBP = women of childbearing potential.

- a. At each clinic visit, whenever feasible, the cognitive and motor assessments should be prioritized. Study visits should be scheduled at approximately the same time each day to ensure that scales are completed at consistent times during the study.
- b. Screening/Baseline assessments may be completed at more than 1 study visit; all assessments must be completed within 28 days.
- c. Subjects who permanently discontinue from the study before completing the Month 36 Visit will be required to return for an Early Termination (ET) Visit.
- d. Written informed consent must be obtained before any study related procedures are conducted.
- e. All prescription and over-the-counter medications that have been taken during the 30 days before Screening/Baseline (i.e., Day 1) through the last study visit will be documented. A complete history of medications taken for the treatment of ALSP will be collected. Prior medical procedures will also be recorded.
- f. COVID-19 assessments will be performed per local guidelines and standard of care at the site.
- g. The “Baseline Screening” (lifetime and last 6 months) C-SSRS form will be completed at Screening to determine eligibility. The “Since Last Visit” C-SSRS form will be completed at Months 6, 12, 18, 24, 30, and 36.
- h. All adverse events/serious adverse events will be monitored until resolution or stabilization.
- i. Attempts will be made to determine the survival status (alive or deceased) of any subject who fails to return for the final visit or who discontinues from the study before completing the 24-month (subjects who withdraw from the study before implementation of Amendment 3) to 36-month (subjects who withdraw from the study after implementation of Amendment 3) observation period. Study staff will contact the subject or the subject’s caregiver by telephone to determine survival status 24 or 36 months, respectively, after the date of the subject’s Screening Visit or at the end of the study, whichever occurs sooner.
- j. Local blood coagulation panel will need to be completed prior to lumbar puncture (LP) for subjects that volunteer to participate in the optional CSF sample collection.
- k. Biomarkers in CSF will be determined in subjects who provide informed consent to participate in an optional CSF Biomarker Sub-study.
- l. The MRI scans may be obtained  $\pm 2$  days before the scheduled visit.
- m. At the investigator’s discretion, the CDR®+NACC-FTLD may not need to be administered if there are no signs or symptoms of cognitive impairment (i.e., normal score on the MoCA) or if the subject does not have a caregiver who has provided informed consent for the study.
- n. The FAQ, NPI-12, and Zarit Burden Interview will not be completed if the subject does not have a caregiver who has provided informed consent for the study.
- o. For subjects who participate in the CSF sub-study and who discontinue from this study to enroll in a VGL101 clinical study, CSF biomarker collection will be performed at the Screening or Baseline Visit of the VGL101 clinical study and will be analyzed as part of both studies. If CSF collection is not included at the Screening or Baseline Visit of the VGL101 clinical study, CSF biomarker collection will be done at the ET Visit of this study.
- p. For subjects who discontinue from this study to enroll in a VGL101 clinical study, blood biomarker collection will be performed once for both the ET Visit of this study and the Screening/Baseline Visit of the VGL101 study and will be analyzed as part of both studies.
- q. For subjects who discontinue from this study to enroll in a VGL101 clinical study, an MRI will be collected once for both the ET Visit of this study and the Screening/Baseline Visit of the VGL101 clinical study and will be analyzed as part of both studies.

## 6.2 Study Assessments

The following are the set of study variables to be collected, following the Schedule of Assessments.

### 6.2.1 Study Entrance and Disease History

- Documentation of CSF1R gene mutation
- Medical/family history and demographics
- Prior/concomitant medications/procedures
- Urine drug screen
- Urine pregnancy test for WOCBP
- COVID-19 assessment

### 6.2.2 Safety Assessments

#### 6.2.2.1 Columbia-Suicide Severity Rating Scale (C-SSRS)

The C-SSRS is a semi-structured tool used to assess suicidal ideation and behavior (Posner et al, 2011). It does not use a simple numerical sum, but rather classifies individuals into different risk categories based on their highest level of ideation and presence of suicidal behavior.

At study baseline, the C-SSRS “Baseline/Screening” version is administered to assess suicidal ideation over two distinct timeframes:

- ***Lifetime Assessment:*** Subjects are asked about the presence and intensity of suicidal ideation at any point in their entire lifetime.
- ***Past 6 months:*** Subjects are also asked about the presence and intensity of suicidal ideation occurring within the past 6 months to capture more recent risk.

For subsequent study visits, the “Since Last Visit” version of the C-SSRS will be used to evaluate any new or ongoing suicidal ideation and behavior that occurred since the subject’s prior visit.

- ***Since Last Visit:*** Subjects are asked about the presence and intensity of suicidal ideation since their last study visit.

The study protocol contains additional detail about using the C-SSRS to determine subject eligibility and continuation in the study, and care for the subject.

#### 6.2.2.2 Physical and Neurological Examinations

A complete physical examination will include measurement of height and weight (Screening/Baseline only) and examination of general appearance and the skin, neck (including thyroid), eyes, ears, nose, throat, heart, lungs, abdomen, lymph nodes, and extremities. Genital, rectal, and breast examination may be excluded if not clinically indicated.

The neurological examination will include assessment of mental status (level of consciousness, orientation, speech, memory, etc.), examination of cranial nerves II-XII, motor examination (muscle appearance, tone, strength, and reflexes), sensory examination, reflexes, coordination, stance, gait, and balance.

Physical and neurological examinations will be conducted at Screening/Baseline and at Months 6, 12, 18, 24, 30, and 36/ET.

#### **6.2.2.3 Adverse Events**

An AE is any unfavorable or unintended sign (including an abnormal laboratory finding), symptom, or disease temporally associated with the use of a medical treatment or procedure that may or may not be considered related to a study procedure.

All AEs and SAEs that are reported by the subject (or, when appropriate, by a caregiver, surrogate, or legally authorized representative) or observed by the investigators from the time the Informed Consent Form (ICF) is signed through the Month 24 Visit (subjects who complete the study before implementation of Amendment 3), the Month 36 Visit (subjects who complete the study after implementation of Amendment 3), or ET Visit will be recorded. All AEs/SAEs will be monitored until resolution or stabilization.

#### **6.2.2.4 Survival Assessment**

Attempts will be made to determine the survival status (alive or deceased) of any subject who is lost to follow-up or who discontinues from the study before completing the 24-month (subjects who withdraw from the study before implementation of Amendment 3) or 36-month (subjects who withdraw from the study after implementation of Amendment 3) observation period. Study staff will contact the subject or the subject's caregiver by telephone to determine survival status 36 months after the date of the subject's Screening Visit or at the end of the study, whichever occurs sooner.

#### **6.2.3 Biomarkers**

Concentration data for pharmacodynamic blood and CSF biomarker variables will be obtained from central testing laboratory.

If more than one concentration is reported for an analyte for a given subject(s) and timepoint(s) (e.g., duplicate analysis inadvertent or otherwise), then the value reported from the batch that included all longitudinal time points for that given analyte and subject will be included in the analysis. Note that this will be identified by the "Assay/Run-ID" that is provided with each batch.

##### **6.2.3.1 Blood Sampling (for Biomarker Analysis)**

Blood samples for NFL will be obtained at Screening/ Baseline and at Months 6, 12, 18 24, 30, and 36/ET. Other exploratory biomarkers (e.g., GFAP) will also be obtained.

### **6.2.3.2 Cerebrospinal Fluid (CSF) Biomarker: Optional Sub-study**

Cerebrospinal fluid samples for NfL, sTREM2, and soluble CSF1R will be obtained at Screening/Baseline and at Months 12, 24, and 36/ET from subjects who provide informed consent to participate in the optional CSF Biomarker Sub-study to provide further insight into the onset and progression of ALSP. Other exploratory biomarkers (e.g., Osteopontin, GFAP) will also be obtained. The completion of these investigations will be based on the results of this or other exploratory work.

### **6.2.3.3 Magnetic Resonance Imaging (MRI)**

Regional brain volume measures and ALSP MRI Severity Scores will be obtained at Screening/Baseline and at Months 6, 12, 18, 24, 30, and 36/ET. Regional brain volume key measures include ventricle volume, total gray matter volume, whole brain volume, corpus callosum thickness, corpus callosum volume, and white matter lesion volume.

The gray matter region will be adjusted (Total Gray Matter Adjusted) to account for tissue identified as gray matter within in the white matter lesion. This will be done using the following equation:

$$\text{Adjusted Total Gray Matter} = \text{Gray Matter} - \text{Gray Matter in White Matter Lesions}$$

## **6.2.4 Cognitive Assessments**

### **6.2.4.1 Montreal Cognitive Assessment (MoCA)**

The MoCA is a screening tool that is used to evaluate cognitive abilities and dementia (Nasreddine et al., 2005). The MoCA evaluates different types of cognitive domains, including orientation, short-term memory, delayed recall, abstraction, visuospatial, and executive functioning; language; and attention. Scores range from 0 to 30.

MoCA Tasks and Points:

- Visuospatial/executive score = 5 points
- Naming score = 3 points
- Attention: Digits forward and backward score = 2 points
- Attention: Letter tapping score = 1 point
- Attention: Serial 7 subtraction score = 3 points
- Language: Repeat score = 2 points
- Language: Fluency score = 1 point
- Abstraction score = 2 points
- Delayed recall only score = 5 points
- Orientation score: 6 items (date, month, year, day, place, city) = 6 points

Additionally, the MoCA can be adjusted for education to help account for differences in cognitive abilities due to education.

- Less than or Equal to 12 years of education (1 points if ‘yes’, 0 point if ‘no’)

When all items are complete, the education-adjusted MoCA is a sum of 11 items:

$$MoCA_{Total} = \sum_{i=1}^{11} Tasks_i + Education$$

Where:

- $Tasks_i$  = cognitive domain tasks (point totals from each of  $i$  tasks)
- $Education$  is a dichotomous variable coded as:
  - 1 indicates less than or equal to 12 years of education
  - 0 indicates > 12 years of education
- Education is collected at each study visit, and the education component from each visit will be used (i.e., the baseline education value will not be carried forward to all subsequent visits)
- The maximum possible score is 30, therefore, if a subject scores 30/30, a point is not added if the subject has 12 years of education or less.

If data are missing from one of the tasks, or if education is missing, MoCATotal will be missing. Because the individual item tasks in the MoCA are not collected in the electronic data, and only the point totals are recorded, available item averaging is not an applicable option. If missing data are >20%, a weighted task averaging will be explored in sensitivity analysis.

The MoCA will be completed at Screening/Baseline and at Months 6, 12, 18, 24, 30, and 36/ET.

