#### 4.1.10 Study Visit

Scheduled subject visits (i.e., Screening/Baseline, Month 6, Month 12, Month 18, Month 24, Month 30, Month 36) will be determined by the visit as specified in the eCRF. That is, scheduled visits will not be windowed and the nominal visit value will be used for analysis.

To utilize as much data as possible for analysis, unscheduled and ET visits will be mapped to a scheduled visit for analysis using windows as defined below, which are to be used for analysis purposes only. Once analysis visit windows are assigned, all visits, including unscheduled and ET visits, are eligible to be flagged as the “analyzed record” within the analysis window. As such, a subject may have more than one record for each analysis visit window. The following rule for determining which record is flagged as the “analyzed record” is as follows:

- When available, data from the scheduled visit is always used.
- If data from the scheduled visit is not available, then data from the unscheduled or ET visit closest to the scheduled visit study day for that analysis window will be used, if available.

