#### **4.3.4 Repeated Measures Analysis**

Mean changes from baseline in Ventricle Volume, MoCA, and CBFS will be analyzed using restricted maximum likelihood-based mixed effects models for repeated measures (MMRM). Separate models will be generated that consider study visit as a categorical variable, and study day as a continuous variable.

In addition the analyses described below, exploratory analyses may be conducted in which additional covariates are added to the previously described MMRM analyses to understand the influence of these covariates and how imbalance in them across may have influenced results. Additionally, if meaningful outliers are identified by the descriptive analyses, the corresponding MMRM analyses may be replicated as a sensitivity analyses in which the outlier observation(s) is omitted.

MMRM analyses may also be performed with percent change from baseline as the dependent variable for the MRI and biomarker endpoints.

Specifically, the following MMRM models will be explored as the primary models of interest:

- Mean change from baseline to last follow-up in Ventricle volume
- Mean changes from baseline to last follow-up in MoCA
- Mean changes from baseline to last follow-up in CBFS

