#### 4.3.4.1 MMRM with Visit as a Categorical Variable

The MMRM model will assess changes from baseline as the dependent variable and include the following parameters:

- ***Subgroup (categorical variable):*** Prodromal, Symptomatic ALSP subjects (Non-HSCT), Symptomatic ALSP (Prior HSCT).
- ***Visit (categorical variable):*** Corresponding to the set of post-baseline scheduled visits for the endpoint as defined in the schedule of assessments.
- ***Baseline score (continuous variable):*** The corresponding baseline value for the dependent variable.
- ***Subgroup × Visit Interaction Effect***
- ***Baseline score × Visit Interaction Effect***

The within-subject covariance will be modeled using a compound symmetric with heterogeneous variance structure (TYPE = CSH). If this analysis fails to converge a simpler compound symmetric structure will be used (TYPE = CS). If this analysis fails to converge the baseline score by visit interaction will be deleted from the model. Denominator degrees of freedom will be determined using the Kenward-Roger approximation.

For each of the 3 subgroups defined above for the categorial Subgroup variable, least squares mean with corresponding SEs, lower and upper bounds of the 95% confidence interval, and p-values will be reported for the within group changes from baseline. The least squares mean difference from the Prodromal subgroup will be similarly presented. Additionally, least squares means and least squares mean difference (versus Prodromal) statistics for the Symptomatic ALSP subgroup (i.e., estimated using a weighted average of the Symptomatic ALSP (Non-HSCT) and Symptomatic ALSP (Prior HSCT) subgroups) may also be estimated.

For each MMRM analysis, a figure will be produced which depicts the least squares mean changes from baseline along with the SE for each of the 3 subgroups by visit.

Sample SAS® code for an MMRM model with study visit as a categorical variable is as follows:

```
PROC MIXED DATA = ADEFF;
  CLASS SUBGR1 (REF='PRODROMAL') AVISIT (REF='BASELINE');
  MODEL CHG = SUBGR1 AVISIT BASE SUBGR1*AVISIT BASE*AVISIT /
  DDFM=KR;
```

```
REPEATED AVISIT / SUBJECT=USUBJID TYPE=CSH;  
LSMEANS SUBGR1*AVISIT / DIFF=ALL CL ALPHA=0.05;  
RUN;
```

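### MoCA scoring takes the education point afresh at each visit and voids the total when education is blank, so a fixed attribute can create false 1-point changes and discard fully scored tests

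*SAP*

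**What the plan says.** SAP 6.2.4.1 lists ten scored tasks and a yes/no education item worth one point for 12 years or less, with the total limited to 30. On the source of that point it says "Education is collected at each study visit" and that "the education component from each visit will be used (i.e., the baseline education value will not be carried forward to all subsequent visits".

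The missing-data rule in the same section begins "If data are missing from one of the tasks, or if education is missing", and the consequence is a missing total. The section explains why it does not rescue incomplete tests: "only the point totals are recorded, available item averaging is not an applicable option". The only fallback is a weighted task-averaging sensitivity analysis if more than 20% of data are missing.

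The section also states: "When all items are complete, the education-adjusted MoCA is a sum of 11 items". The formula that follows sums tasks from 1 to 11 and then adds Education.

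SAP 4.3.4 names "Mean changes from baseline to last follow-up in MoCA" among the three repeated-measures models of primary interest. SAP 4.4 puts Month 12 change in MoCA, paired with Month 12 change in ventricle volume, among the correlations of primary interest.

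**The concern.** The education point adjusts for differences between people. For change within a person it should drop out, and it does if the same value is used throughout. Letting it vary by visit has two consequences.

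- **False change.** If one visit records 12 years or less and another records more, the MoCA change moves by one point although every task score is the same.
- **Lost data.** If education is blank at a visit where all ten tasks were scored, the total is discarded, even when education is recorded at every other visit. A blank at baseline removes all of that subject's change scores unless another record falls in the baseline window (days -28 to 1, SAP Table 2).

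The SAP's reason for not filling gaps concerns task items that are not held electronically. It does not apply to education, which is a separate field collected at each visit. The SAP is also more lenient elsewhere: it recovers limited missing items for the CDR+NACC-FTLD sum of boxes, CBFS, FAQ, NPI-12 and ZBI. For MoCA it drops a complete test over a value that could be recovered without imputation.

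At stake is some precision, and a little noise, in an outcome of primary interest that is also meant to support an integrated analysis with the Phase 2 study (SAP 4.1.1).

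**Working it through.** **1. The plan's own figure.** Listed task points: 5 + 3 + 2 + 1 + 3 + 2 + 1 + 2 + 5 + 6 = 30, over 10 tasks. This reproduces the stated maximum of 30. The eleventh item is education, so a sum over 11 tasks plus Education either counts education twice or refers to a task that does not exist.

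**2. The rule applied to unchanged performance.** Total = min(30, tasks + education), missing if education is blank. Task scores are identical at baseline and follow-up; raw scores tested are 12, 20, 25, 29 and 30.

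| Education point, baseline → follow-up | Change at raw 12, 20, 25, 29 | Change at raw 30 |
|---|---|---|
| 0 → 1 | +1 | 0 (cap) |
| 1 → 0 | -1 | 0 (cap) |
| blank at either visit | missing | missing |
| same at both | 0 | 0 |

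With one education value per subject, only the last row can occur.

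**3. Size.** The documents give no blank or discordance rates. I assume a per-entry rate q of 1% to 10%, independent across visits, with all tasks scored.

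- Change score lost (blank at baseline or follow-up): 1 - (1 - q)².
- SE inflation, Month 12 analysed alone: a fraction (1 - q)² of changes remains, so 1/(1 - q) - 1.
- SE inflation from blank baselines only: 1/√(1 - q) - 1.
- SE inflation, repeated-measures model with visit means: expected information = (1 - q) × the sum, over patterns of observed visits, of P(pattern) × the inverse of the observed covariance. The correlation form is the planned one: "The within-subject covariance will be modeled using a compound symmetric with heterogeneous variance structure (TYPE = CSH". Covariance is treated as known, and the ratio does not depend on the visit variances. Assumed: correlation of changes 0.5, 0.7 or 0.9; 2, 4 or 6 post-baseline visits; data otherwise complete.
- Change shifted by one point (each entry wrong with probability q): 2q(1 - q).
- SE inflation from shifts: √(1 + 2q(1 - q)/SD²) - 1, with the SD of change assumed 3 to 5 points.

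| q | Changes lost | SE, Month 12 alone | SE, repeated-measures model | SE, blank baselines only | Changes shifted | SE from shifts (SD 5 to 3) |
|---|---|---|---|---|---|---|
| 1% | 2.0% | +1.0% | +0.56 to 0.89% | +0.5% | 2.0% | +0.04 to 0.11% |
| 2% | 4.0% | +2.0% | +1.1 to 1.8% | +1.0% | 3.9% | +0.08 to 0.22% |
| 5% | 9.8% | +5.3% | +2.9 to 4.6% | +2.6% | 9.5% | +0.19 to 0.53% |
| 10% | 19.0% | +11.1% | +6.1 to 9.9% | +5.4% | 18% | +0.36 to 1.0% |

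The low end of the model column is 6 visits with correlation 0.9; the high end is 2 visits with correlation 0.5. More than half of the model loss comes from blank baselines, because other visits cannot stand in for them. With 60 subjects all reaching Month 12, q = 1% loses 60 × 0.0199 ≈ 1.2 change scores there, and q = 10% loses 60 × 0.19 = 11.4.

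**4. Whether anything else in the SAP repairs this.** SAP 4.1.10 offers a substitute record: "If data from the scheduled visit is not available, then data from the unscheduled or ET visit closest to the scheduled visit study day". That helps only if such a record exists in the window. The 20% sensitivity analysis averages tasks, not education. The 3 SD outlier screen in SAP 4.1.12 would generally not flag a 1-point shift. No provision reconciles education across visits.

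**The case against.** The rule is explicit and pre-specified, and scoring each visit from its own record is a recognisable convention. Nothing in the documents shows that any entry is blank or discordant. The upper figures need one in ten answers to a single yes/no item to be blank or wrong, which is pessimistic. At 1%, about one Month 12 change is lost and the SE rises by less than 1%. The study is exploratory, with no multiplicity control (SAP 4.1.6) and no power calculation (SAP 4.1.4). Entry is from age 18, so a young subject could truly pass 12 years of education. The SE illustration covers the visit-based model only, not the study-day model in SAP 4.3.4.2, and it omits subgroups, the baseline-by-visit term and dropout. The Phase 2 SAP is not available, so changing this SAP alone could create a mismatch.

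Most of this stands as a limit on size. The harm is conditional, the low end of the range is the more plausible, and loss is smaller if blanks fall at visits that also have unscored tasks. None of it supports the rule itself: a true crossing of 12 years would still not be a change in cognition, and a visit-specific education point adds nothing to a change score. The Phase 2 point is a reason to state one derivation for both studies.

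A single value per subject has one weakness. An uncaught wrong baseline entry would cancel from change (apart from the cap) but would remain in the baseline covariate and in the cross-sectional correlations. This is why conflicting entries should be queried.

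**Conclusion.** The concern holds. Both consequences follow directly from SAP 6.2.4.1, and no other provision removes them. The effect is minor: under assumed blank rates of 1% to 10%, model precision for the Month 12 mean worsens by roughly 0.6% to 10%, mainly through blank baselines, and false 1-point changes add about 1% or less to the SE. These are illustrations that rest on the assumed rates, on independence across visits, and on education being effectively fixed in adults, which is an inference and not a statement in the documents. No conclusion of the study is threatened. The change is still worth making because the outcome is one of primary interest, the current rule has no benefit for change from baseline, and the remedy uses data already collected.

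**What to change.** In SAP 6.2.4.1:

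1. Derive one education value per subject: the baseline entry or, if that is blank, the first non-missing entry from a later visit. Query discordant entries before the database freeze.
2. Apply that value at every visit. Do not set the total to missing because education is blank at one visit when it is known from another.
3. If education is blank at every visit, compute change from the unadjusted ten-task total and use that baseline total as the covariate. It is at most 1 point below the adjusted one.
4. Report change in the unadjusted ten-task total as a sensitivity analysis. It does not depend on education or on truncation of the education point, although the scale still has a maximum of 30.
5. State which derivation the integrated analysis uses, after checking the Phase 2 SAP, so that both studies score MoCA alike. This matters most for assessments collected once and analysed in both studies (Protocol 4.1).
6. Correct the formula to ten tasks plus Education, capped at 30.

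Keep the missing-task rule and its 20% sensitivity analysis as they are.

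Cost: SAP wording, a short derivation with its routine verification, any site queries on conflicting entries, and one sensitivity table. No new data collection.
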